Given the above considerations, the benefit-risk assessment in this highly compromised AML patient population is considered favourable for this trial and the potential benefit of therapy with BI 836858 in combination with decitabine is expected to outweigh the treatment-related risks.

3. DESCRIPTION OF DESIGN AND TRIAL POPULATION

3.1 OVERALL TRIAL DESIGN AND PLAN

The trial will be performed according to an open-label design for both, Phase I and Phase II part. The data obtained from the Phase I part of the trial will be used to determine the MTD (or a Recommended Extension Phase I Dose (RExP1D), see [Section 4.1.3](#) for details) of BI 836858 in combination with decitabine based on a Bayesian logistic regression model (BLRM) with overdose control.

Based on data from the Phase I Extension it will be decided if the RExP1D will become the Recommended Phase II Dose (RP2D) of BI 836858, or if additional patients need to be enrolled in existing or additional dose escalation cohorts to determine the RP2D.

In Phase II, this trial will explore efficacy and safety of BI 836858 in combination with decitabine *versus* decitabine monotherapy in a randomized manner.

In both phases of the trial, a group of experts (in Phase I a trial-internal Safety Monitoring Committee (SMC) and in Phase II a Sponsor-internal DMC) will be responsible for continuous assessment of the trial data as described in this protocol and the DMC charter (filed in the Trial Master File) to ensure overall safety of the patients treated. In Phase I, the SMC's responsibility will be the recommendation of the dose escalation and de-escalation steps and the monitoring of the quality of the data. In Phase II the DMC will provide advice about the conduct of the trial and the integrity of the data.

After having provided informed consent and after a screening period of up to 14 days, eligible patients will be allocated to treatment by Interactive Response Technology (IRT) to the respective dose cohort or treatment group. The patients will be asked to remain under the Investigator's or their staff's supervision during the duration of administration of decitabine as well as BI 836858. The patients will visit the site at regular intervals for assessment of safety and efficacy and for collection of blood for analysis of the PK of BI 836858 and decitabine. Treatment will continue until progression or relapse of the underlying AML or if patients and/or Investigators decide to discontinue therapy according to the criteria as defined in [Section 3.3.4](#).

In Phase I patients will be followed up at regular intervals for approx. 6 months after end of treatment or until death, whichever occurs earlier. In Phase II, after the last administration of any of the two trial drugs the patients will be followed up at regular intervals for OS until death or until the end of the whole trial, whichever occurs earlier (refer to [Section 6.2.3](#)).

The results of the trial will aid in the decision-making on the further development program of BI 836858 in AML.

Phase I:

In the Phase I Dose Escalation, patients ≥ 65 years of age with previously untreated AML, who are considered ineligible for standard intensive therapy, or patients ≥ 18 years of age

with relapsed or refractory AML will be assigned to the respective dose cohort that is being investigated when the patient is entering the trial. The Phase I Dose Escalation will be guided by a Bayesian logistic regression model (BLRM) with overdose control (refer to [Section 7](#)). As new patient safety information becomes available, the BLM estimates the MTD by updating estimates of the probability of observing a DLT in the first cycle for each dose level in the study. At any time in the trial, it will not be permitted to escalate to a dose which does not fulfil the escalation with overdose control (EWOC) criterion (refer to [Section 7](#)). Dose escalation will be restricted to a maximum of 100% from the previous dose.

At least 3 patients will be required for every dose escalation cohort, (refer to [Section 7](#)). In the case that only 2 patients are evaluable and neither has experienced a dose-limiting toxicity within Cycle 1 (patient has received at least 3 administrations of BI 836858 and reached end of Cycle 1, i.e. patient is eligible to continue trial treatment on Day 1 of Cycle 2 at the latest on Day 57 after start of Cycle 1, refer to [Section 5.3.1](#)), then dose escalation can occur based on these 2 patients.

After all patients in a cohort have either experienced a DLT or have been observed for at least one cycle without experiencing a DLT, the Bayesian logistic regression model (BLRM) will be updated with the newly accumulated data. The overdose risk will then be calculated for each dose and escalation will be permitted to all doses fulfilling the EWOC criterion and the additional 100% escalation rule. Based on the model and on additional information (e.g. PK, pharmacodynamics, AE, patient profiles), the members of the SMC will determine the next dose level and cohort size.

If DLTs are observed in the first two consecutive patients of a previously untested dose level, subsequent enrolment to that cohort will be stopped. The BLM will be re-run to confirm that the dose level still fulfils the EWOC criterion. Based on this information, the SMC will evaluate whether the next patients will be enrolled on the same dose level, or if they will be enrolled on a lower dose level.

The SMC may recommend stopping the dose escalation phase after the criterion for MTD (refer to [Sections 5.3.2](#) and [7.1](#)) is fulfilled. Further patients may be included to confirm this MTD estimate. If no DLT is observed at a dose of which the efficacy is considered sufficient, the SMC may recommend to include an additional number of patients at the same dose level and to declare this dose as the RExP1D.

Based on the totality of data (PK, pharmacodynamics, biomarker and safety) the SMC may also recommend treating additional patients prior to the Phase I Extension part with the MTD (or RExP1D) or higher doses of BI 836858 in combination with the standard treatment schedule of decitabine. The number of patients to be treated and the dose of BI 836858 to be tested will be discussed and recommended by the SMC.

In the Phase I Extension part of the trial, up to 30 previously untreated patients with AML who are ≥ 65 years old and considered ineligible for standard intensive therapy, will be allocated subsequently into two cohorts. Up to 15 patients will be allocated to Cohort A, i.e. treatment with BI 836858 and decitabine 20 mg/m² for 10 consecutive days (decitabine

intensive treatment schedule) and up to 15 patients will be allocated to Cohort B, i.e. treatment with BI 836858 and decitabine 20 mg/m² for 5 consecutive days (decitabine standard treatment schedule).

If deemed necessary by the Sponsor and the SMC, based on a comprehensive review of available clinical trial data, biomarker results (including CD33 receptor saturation) and PK-results, additional patients may be enrolled after the extension cohorts into pre-existing or new dose escalation cohorts to further optimize the BI 836858 dose and determine the RP2D. Dose escalation steps for additional dose cohorts will be defined according to the rules as outlined for the phase I dose escalation part of this protocol.

The decitabine schedule to be used for each cohort will be determined by the Sponsor in agreement with the SMC and documented in the SMC meeting minutes.

A final recommendation on the RP2D dose of BI 836858 and on the duration of treatment with decitabine will be given after Phase I safety data of both, the dose escalation part as well as the extension part, will have been summarized and reviewed by the SMC.

Prior to the initiation of Phase II, safety and preliminary PK results will be analyzed and documented in a safety analysis report or lean interim Clinical Trial Report (CTR). This Phase I safety analysis report or lean interim CTR will be sent to competent authorities/ethic committees. A summary of safety and efficacy endpoints and determination of the RP2D will be included in this report.

The RP2D of BI 836858 with either the standard 5 day treatment schedule or the intensive 10 day treatment schedule of decitabine will be used in the combination treatment Arm 1 of the Phase II of the trial.

After completion of recruitment to Phase I Extension Cohort A and Cohort B, the recruitment to this trial is discontinued.

Phase II:

In Phase II, previously untreated patients with AML, who are \geq 65 years old and considered ineligible for standard intensive therapy will be randomized in a 1:1 manner to investigate efficacy and safety of BI 836858 at RP2D in combination with decitabine *versus* decitabine monotherapy. The screening phase may be up to 14 days; therefore, the first dose of trial treatment should occur no more than 15 days after the informed consent is signed. The type of AML (*de novo*, secondary AML) is an important prognostic factor ([R07-2768](#)); therefore, patients will be stratified by type of AML to ensure a balanced distribution of this prognostic factor between treatment groups. A total of approx. 100 patients, 50 in each arm, will be enrolled in Phase II.

Patients will be enrolled in the trial once they have signed the informed consent form and entered into the trial once they have been confirmed to meet the inclusion and exclusion criteria.

Proprietary confidential information © 2019 Boehringer Ingelheim International GmbH or one or more of its affiliated companies

Patients will be treated within the assigned cohort or treatment arm until progression/relapse or until patients and/or Investigators decide to discontinue therapy (refer to [Section 3.3.4](#)). No patients will be allowed to continue trial treatment and switch or be entered into another part of this trial.

The overall structure of the trial is described in [Figures 3.1: 1](#). (Phase I) and [3.1: 2](#) (Phase II)

[figure not shown]

Figure 3.1: 1

Overall structure of the trial Phase I

[figure not shown]

Figure 3.1: 2

Overall structure of the trial Phase II

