For the optional Dose Escalation Cohorts following Extension Cohorts A and B, a time interval of at least 3 days must have elapsed between the 1st administration of BI 836858 for each new patient treated. This means that start of trial treatment with decitabine (Cycle 1_Day 1) for the next subsequent patient may occur at the earliest on Cycle 1_Day 4 of the previous patient.

For any dose escalation cohort, at least 3 patients will be required (refer to [Section 7](#)). However, in the case that only 2 patients are evaluable and neither has experienced a DLT within the Cycle 1 (i.e. patient has received at least 3 administrations of BI 836858 and reached end of Cycle 1; please refer to [Section 5.3.2](#)) then dose escalation can occur based on these 2 patients.

After all patients in a cohort have either experienced a DLT or have been observed throughout Cycle 1 (refer to [Section 5.3.2](#)) without experiencing a DLT, the Bayesian model will be updated with the newly accumulated data. The overdose risk will then be calculated for each dose, and escalation will be permitted to all doses which fulfil the EWOC criterion and the additional 100% escalation rule. Based on the model and on additional information (e.g. PK, pharmacodynamics, AE, patient profiles), the members of the Safety Monitoring Committee (SMC) will recommend the next dose level and cohort size.

If DLTs are observed in the first two consecutive patients of a previously untested dose level, subsequent enrolment to that cohort will be stopped. The Bayesian logistic regression model (BLRM) will be re-run to confirm that the dose level still fulfils the EWOC criterion. Based on this information, the SMC will evaluate whether the next patients will be enrolled on the same dose level, or if they will be enrolled to a lower dose level.

The MTD may be considered reached if the following criteria are fulfilled:

- 1) The posterior probability of the true DLT rate in the target interval [0.16, 0.33] of the MTD is above 0.50, OR
- 2) At least 15 patients have been treated in the study, of which at least 6 were treated at the MTD.

If no DLT is observed at a dose of which the efficacy is considered sufficient, the SMC may decide to include additional patients at this dose level and to declare this dose as the RExP1D.

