Deaths occurring ≥ 7 days following completion of treatment cycle while cytopenic; with an aplastic or hypoplastic bone marrow obtained within 7 days of death, without evidence of persistent leukemia. Completion of treatment cycle is defined as reaching of Day 28 of the cycle.
- Death from indeterminate cause
Deaths occurring before completion of a treatment cycle, or < 7 days following its completion; or deaths occurring ≥ 7 days following completion of treatment course with no blasts in the blood, but no bone marrow examination available. Completion of treatment cycle is defined as reaching Day 28 of the cycle.

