5.3.1 Dose limiting toxicity (DLT)

DLT is defined as any non-disease-related non-hematological AE of CTCAE grade 3 or higher.

Expected non-hematological disease-related AEs will not be regarded as a DLT. These include complications resulting from hematological AEs such as:

- Bleeding and complications from bleeding due to thrombocytopenia as defined by the Investigator
- Infection and complications from infections due to neutropenia as defined by the Investigator
- Constitutional symptoms due to anaemia as defined by the Investigator

Infusion-related reactions (IRR) associated with the administration of BI 836858 should be reported as Adverse Event of Special Interest (AESI, refer to [Section 5.3.8.1](#)), but will not be regarded as a DLT. The exception is anaphylaxis which occurs despite premedication with glucocorticoid or which does not resolve with glucocorticoid (i.e. such cases of anaphylaxis will be regarded as a DLT).

Patients who do not receive at least 3 administrations of BI 836858 due to BI 836858-related toxicity are considered to have developed a DLT. If Cycle 2 is not started until 57th day from Day 1 of Cycle 1 as a result of drug-related AE, this AE is considered as DLT (i.e. treatment delay of \geq 4 weeks of the start of Cycle 2 due to drug-related AE). Patients who do not experience a DLT but do not receive all 3 planned administrations of BI 836858 during Cycle 1 for reasons other than toxicity or tolerability will not be evaluable for DLT and cannot be used to establish the MTD.

Infection will not constitute a DLT unless it is felt that the infection resulted from unexpectedly complicated myelosuppression; degree of severity and/or duration as assessed by the Investigator.

Since patients with refractory leukemia have infections and bleeding complications from myelosuppression, these events will not be considered as DLT unless they occur in the setting of prolonged myelosuppression from the combination treatment. Prolonged myelosuppression is defined as ANC < 1000/ μ L and PLT < 100,000/ μ L by day 56 of Cycle 1 in the setting of bone marrow showing < 5% blasts, without evidence of persistent cytogenetic abnormalities or minimal residual disease by flow cytometry. In case persistent cytogenetic abnormalities or immunophenotypic evidence of leukemia is present, myelosuppression would be considered secondary to leukemia even if morphology shows < 5% blasts.

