6.2.2 Treatment period

The first trial drug administration should occur as soon as possible after the randomization / treatment allocation. A treatment cycle is defined as 28 days. If initiation of a subsequent cycle is delayed due to medical reasons, visits beyond Day 28 may be necessary. Additional unscheduled visits may be performed at the Investigator's discretion if medically indicated, but at least weekly; these unscheduled visits should also be reported in the eCRF.

An End of Cycle (EOC) visit will be performed at the end of each treatment cycle, i.e. on Day 29 (± 3 days). A subsequent treatment cycle should not start earlier than on the 29th day of the precedent cycle (if e.g. the previous cycle started on a Tuesday the next cycle will start earliest on a Tuesday 4 weeks later).

Day 29 (Visit 4, EOC) can be the same day as Day 1 (Visit 1) of the next treatment cycle if the patient is eligible to receive further treatment without delay. In that case Day 29 becomes Day 1 of next cycle and all procedures and assessments as indicated for Day 29 and Day 1 of the next cycle should be performed.

During Phase I and Phase II the decitabine treatment schedule for Cycles ≥ 2 will be individually customized depending on the blast count at the end of previous cycle. For details on the treatment schedules refer to [Table 4.1.3.1: 1](#) for patients treated in the Phase I Dose Escalation and to [Table 4.1.3.2: 1](#) for patients treated in the Phase I Extension and Phase II.

Refer to [Section 4.1.4.2](#) for treatment delay and resuming subsequent cycle of treatment.

With the aim to minimize the burden for trial participants, after approval of Protocol version 7.0, the mandatory protocol procedures are reduced for all patients who continue to receive trial medication in treatment cycles >7 . Refer to updated [Flow Chart](#) for specific requirements during treatment period.

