5. ENDPOINTS(S)

5.1 PRIMARY ENDPOINT(S)

Phase I

The primary endpoints in the Phase I part of the trial are the maximum tolerated dose (MTD) and the number of subjects with of dose limiting toxicity (DLT) during the MTD evaluation period.

Maximum tolerated dose (MTD):

The MTD is defined as the highest dose of BI 836858 (in combination with decitabine) with less than 25% risk of the true DLT rate being above 33% during the MTD evaluation period.

MTD evaluation period:

The MTD evaluation period is defined as the time from the first administration of study drug to the start of the second treatment cycle or the end of 30-day residual effect period after last administration of study drug, whichever comes first. Subjects who were replaced during the MTD evaluation period will not be considered for MTD determination. The subjects who are completed the MTD evaluation period without being replaced are considered MTD evaluable.

In case a subject has not completed the required number of administrations due to BI 836858 related toxicity, he/she will not be replaced and this will be considered as DLT. However, subjects who have not completed the required number of administrations of BI 836858 for reasons other than BI 836858 related toxicity will be replaced. Subjects who were replaced during the MTD evaluation period will not be considered for MTD

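### The model update rule, the DLT definition and the SAP's MTD evaluation period use different observation windows, so a patient whose DLT status is still open can be modelled as DLT-free

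*Protocol*

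**What the plan says.** **Model update.** Protocol Section 3.1 allows the BLRM to be updated, and the next dose to be chosen, "After all patients in a cohort have either experienced a DLT or have been observed for at least one cycle without experiencing a DLT". Section 4.1.3.1 repeats the rule in other words, "After all patients in a cohort have either experienced a DLT or have been observed throughout Cycle 1", and points to Section 5.3.2, which names no day. Section 6.2.2 states: "A treatment cycle is defined as 28 days".

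**DLT definition.** Section 5.3.1 makes the delay itself a criterion: "If Cycle 2 is not started until 57th day from Day 1 of Cycle 1 as a result of drug-related AE", the event counts as a DLT. It also lets infection or bleeding count when it occurs in prolonged myelosuppression, which is judged "by day 56 of Cycle 1 in the setting of bone marrow showing < 5% blasts".

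**Where Day 57 appears in Section 3.1.** Just before the update rule, Section 3.1 explains the end of Cycle 1 as eligibility for Cycle 2 by Day 57 at the latest. That explanation sits inside the exception that lets escalation proceed on two evaluable patients. When Section 4.1.3.1 repeats the exception, the Day 57 wording is absent.

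**Final analysis.** SAP Sections 5.1, 6.1 and 7.4 run the MTD evaluation period from first administration "to the start of the second treatment cycle or the end of 30-day residual effect period", whichever comes first. Protocol Section 5.1.1 gives yet another time frame for the same endpoint: the end of Cycle 1, glossed as the end of the residual effect period (REP) and up to about 12 months.

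**The concern.** A patient who reaches Day 28 without a DLT, but whose Cycle 2 is on hold for a drug-related event, satisfies the general update rule. Under Section 5.3.1 the same patient's DLT status is still undecided. Nothing in the general rule keeps that patient out of the likelihood as a non-event.

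The error has one direction only: an open status counted as no DLT can later become a DLT, but not the reverse. The overdose criterion is the hard limit on escalation, and it would be computed on an incomplete endpoint for the patients who recover most slowly. A cohort could be opened on a count that the definition later revises. MTD and first-cycle DLTs are also the Phase I primary endpoints, so the same ambiguity reaches the final analysis through the SAP window.

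**Working it through.** **1. The windows side by side**

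| Use | Source | Closes at |
|---|---|---|
| Model update, general rule | Protocol 3.1 and 4.1.3.1, with 6.2.2 | one cycle of 28 days |
| Exception for two evaluable patients | Protocol 3.1 | eligible for Cycle 2, Day 57 at the latest |
| DLT through delayed Cycle 2 | Protocol 5.3.1 | Day 57 |
| DLT through infection or bleeding in prolonged myelosuppression | Protocol 5.3.1 | Day 56 |
| Primary endpoint time frame | Protocol 5.1.1 | end of Cycle 1, or end of REP |
| MTD evaluation period | SAP 5.1, 6.1, 7.4 | start of Cycle 2 or end of 30-day REP, whichever is first |

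**2. Calendar arithmetic**

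- Cycle 2 may start on Day 29 at the earliest. Open interval: 57 − 29 = 28 days, about 4 weeks.
- The last nominal BI 836858 infusion in Cycle 1 is on Day 23 (Section 4.1.3.1). If Cycle 2 does not start, the SAP window closes at about 23 + 30 = Day 53, before Day 56 and Day 57. For the REP to reach Day 57, the last infusion would have to fall on Day 27 or later (27 + 30 = 57).

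**3. Reproducing the plan's model**

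Inputs: the Section 7.1.1 model and the mixture priors of Table 7.1.1: 3. With decitabine at its reference dose of 20 mg/m²:

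- logit(π₁) = log α₁ + β₁ log(d/160); logit(π₂) = log α₂
- π⁰ = π₁ + π₂ − π₁π₂; odds(π) = odds(π⁰) × exp(η d/160), with η ~ N(0, 0.993²)
- each prior draw is weighted by the product of π^r (1 − π)^(n − r); P(OD) is the weighted share with π ≥ 0.33; a dose is eligible if P(OD) < 0.25.

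With 3,000,000 draws, prior P(OD) at 20, 40, 80, 160 and 320 mg is 0.135, 0.190, 0.312, 0.538 and 0.669. Table 7.1.1: 4 prints 0.133, 0.186, 0.312, 0.537 and 0.665.

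**4. One open patient who later proves to be a DLT, from the planned 20 mg start**

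The "before" and "after" columns give Table 10.2: 1 as printed.

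| Scenarios | DLT data | Before | After | Permitted dose |
|---|---|---|---|---|
| 2.1 to 3.1 | 20 mg: 1/3 to 2/3 | 40 mg, P(OD) 0.222 | none (0.417 at 20 mg) | changes |
| 9 to 10 | 20 mg: 1/3; 40 mg: 0/3 to 1/3 | 80 mg, 0.201 | 40 mg, 0.239 | changes |
| 1.1 to 2.1 | 20 mg: 0/3 to 1/3 | 40 mg, 0.076 | 40 mg, 0.222 | unchanged |
| 4 to 5 | 20 mg: 0/3; 40 mg: 0/3 to 1/3 | 80 mg, 0.111 | 80 mg, 0.244 | unchanged |

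The recoded model agrees on the two rows that change:

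- Scenario 2.1 gives 0.226 at 40 mg; scenario 3.1 gives 0.416 at 20 mg and 0.506 at 40 mg.
- Scenario 9 gives 0.207 at 80 mg; scenario 10 gives 0.243 at 40 mg and 0.412 at 80 mg.

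For scenario 5 at 80 mg it gives 0.259 against the printed 0.244. That is close, but on the other side of 0.25, so I take the printed result and rest nothing on that row.

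**5. Handling matters before the status is known**

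If the open patient in scenario 2.1 is left out, the data are 1/2 at 20 mg. P(OD) is then 0.217 at 20 mg and 0.295 at 40 mg, so the model would not permit 40 mg. Counted as DLT-free, the same patient makes 40 mg eligible.

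**The case against.** **A longer reading of Cycle 1 is available.** Section 5.3.1 speaks of Day 56 as a day of Cycle 1, Section 3.1 asks for at least one cycle, and Section 6.2.2 goes straight on to visits beyond Day 28. The statement "Completion of treatment cycle is defined as reaching Day 28 of the cycle" belongs to the classification of deaths, not to DLTs. This stands as evidence of intent. A reader might infer that the plan directs open patients to be counted as DLT-free; it does not. It fails to prevent it.

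**One missed DLT does not always matter.** A reader might infer that it does from scenarios 1.2 and 2.2 (0/3 against 1/3 at 40 mg). Those belong to the alternative 40 mg start, and the 20 mg path includes two printed cases with no change. The two printed reversals used here both need a DLT already counted.

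**The exposed group is narrow.** Only drug-related delay qualifies. Non-disease-related, non-haematological events of grade 3 or higher are normally DLTs when they occur. Section 4.1.4.2 lets many patients proceed despite cytopenia. A reader might assume a 20 to 40% rate of delay and obtain 1 − 0.8³ = 49% to 1 − 0.6³ = 78% of three-patient cohorts affected. No such rate is in the documents, and the sum counts any delay, so it does not measure this risk.

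**Safeguards exist.** The SMC also sees adverse events and patient profiles, and Sections 5.3.2 and 7.3.1 re-run the model with DLTs from all cycles. These help later decisions but cannot undo a cohort already opened. The re-run is also worded for patients who receive more than one cycle.

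**The SAP might date such a DLT by onset of the event**, which could fall before Day 53. That would resolve the delay route, but SAP Sections 5.1 and 7.4 do not say so.

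**Escalation is over.** The synopsis gives 16 escalation patients and recruitment is discontinued, so new wording cannot change past decisions. This limits the practical gain but leaves the primary analysis affected.

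**Conclusion.** The point holds as a misalignment of windows. The general update rule can be met at Day 28, two DLT routes are settled only at Day 56 or 57, and the SAP window can close at about Day 53. A delay-based DLT can therefore be missing from the interim model and can fall outside the period that defines the primary endpoint.

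The bias is always towards too few DLTs. Its size depends on the data: one patient can remove all eligible doses (scenario 2.1 to 3.1) or lower the permitted dose from 80 to 40 mg (9 to 10), or change nothing (1.1 to 2.1, and 4 to 5 as printed).

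The conclusion assumes the 28-day meaning of a cycle in the general rule. The Day 53 figure further assumes a last infusion on Day 23 and no start of Cycle 2 by then. No claim is made about how often this arises, or that it did arise in this trial.

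**What to change.** 1. Reconcile Protocol Sections 3.1 (general rule and exception), 4.1.3.1, 5.1.1 and 5.3.1 with SAP Sections 5.1, 6.1 and 7.4, so that all use one DLT observation window consistent with the trial's own Section 5.3.1 definition.
2. State that a patient whose DLT status is still open under that definition is not entered in the likelihood as DLT-free, and say how such a patient is handled at a model update.
3. Align the SAP's MTD evaluation period so that a DLT confirmed at Day 56 or 57 is counted in the primary analysis, and state how it is dated.
4. As escalation is complete, check the 16 escalation patients and the archived SMC outputs (Protocol Section 7.4) for anyone modelled as DLT-free while open. Report the result, with a re-run of the model if any is found.

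Cost: wording changes and a small data check. In any further escalation cohort, a model update could wait up to about 4 weeks, and only when a patient's Cycle 2 is delayed.
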